Initially, 6 patients will be enrolled into a safety cohort for each study arm. The 6-patient safety cohort will be evaluated for the occurrence of DLTs during the first 28 days of combination treatment. For patient in Arm A during the run-in period with BBI608 monotherapy, the same DLT rules as for the combination therapy will apply. Enrollment will be held if ≥ 2 patients are unable to undergo resection due to DLTs. Enrollment will also be held if ≥ 2 patients have an unexpected surgical complication.

For a given arm, if ≥ 2 out of 6 patients experience a DLT, then the BBI608 dose will be reduced for all patients in that arm to the next lower dose level of 240mg twice daily. Furthermore, an additional 6-patient safety cohort in that study arm will be enrolled at the reduced dose-level and evaluated for DLT as described below.

Recommended Phase 2 Dose (RP2D) will be defined as the dose-level evaluated at which ≤ 1 of 6 patients per cohort experiences a DLT.

An additional 24 patients may be enrolled at RP2D in each arm.

For both study arms, cycle length will be 28 days. Combination-therapy cycles will consist of BBI608 administration daily for 28 days and TMZ administration on days 1-5 of each cycle.

Tumor assessments using RANO criteria will be performed every eight weeks from the initiation of combination therapy with BBI608 and TMZ, or otherwise as clinically indicated.

Number of Subjects with DLT at a Given Dose Level for a Given Study Arm	Dose De-escalation Decision Rule
≤ 1 out of 6	This dose level will be considered RP2D for the combination regimen (BBI608+TMZ)
≥ 2 out of 6	Initial dose level will be reduced to a dose chosen by the Investigator and BBI medical monitor. Six (6) additional subjects will be entered at this lower dose level and evaluated for DLT over the first 28 days of combination therapy.

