9.3 Response Criteria

Radiographic response should be determined in comparison to the tumor measurement obtained at pretreatment baseline for determination of response, and the smallest tumor measurement at either pretreatment baseline or after initiation of therapy for determination of progression. For patients in Arm A who undergo surgical resection, the post-operative baseline scan (performed 48-72 hours after surgery) should be used for response assessment.

Response criteria are outlined below. In the event that the radiographic changes are equivocal and it is unclear whether the patient is stable or has developed progressive disease, it is permissible to continue treatment and observe the patient closely, for example at 4-week intervals. If subsequent imaging studies demonstrate that progression has occurred, the date of progression should be the date of the scan at which progression was first suspected.

Complete Response*

Requires ALL of the following:

1. Complete disappearance of all enhancing measurable and non-measurable disease sustained for at least 4 weeks.
2. No new lesions.
3. Stable or improved non-enhancing (T2/FLAIR) lesions.
4. Patients must be off corticosteroids (or on physiologic replacement doses only).
5. Patients must be stable or improved clinically.[#]

Partial Response*

Requires ALL of the following:

1. Greater than or equal to 50% decrease compared to baseline in the sum of products of perpendicular diameters of all measurable enhancing lesions sustained for at least 4 weeks.
2. No progression of non-measurable disease.
3. No new lesions.
4. Stable or improved non-enhancing (T2/FLAIR) lesions on same or lower dose of corticosteroids compared to baseline scan.
5. The corticosteroid dose at the time of the scan evaluation should be no greater than the dose at time of baseline scan.
6. Patients must be stable or improved clinically.#

Stable Disease

Requires ALL of the following:

1. Does not qualify for complete response, partial response, or progression.

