10 PLANNED STATISTICAL METHODS

10.1 General Considerations

Categorical variables will be summarized as the number and percentage of patients in each category. Continuous variables will be summarized by the mean, standard deviation, median, minimum, and maximum.

The primary population for the efficacy endpoints will be the Per Protocol population defined as the population of patients who have been treated with at least 80% of 1 complete cycle of BBI608 and TMZ. Analyses will also be performed on the Intent-to-Treat (ITT) population in each arm. The primary endpoint is PFS-6, defined as the proportion of patients with PFS (i.e. absence of documented objective progression or death) at 6 months after enrollment.

For each of the study arms, the secondary endpoints will include OS, defined as the interval between the date of patient enrollment until death; PFS, defined as the interval between the date of patient enrollment and objective disease progression or death; ORR, the proportion of patients with a documented complete response or partial response according to the RANO criteria; and DCR, the proportion of patients with a documented stable disease, partial response or complete response according to RANO criteria.

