8.2.2.2. Progression Free Survival at 6 months (PFS-6, Phase 1 and Phase 2)

PFS data will be analyzed by arm. PFS summary in Arm B will be provided only when the number of patients in that arm is at least 10. The same rule applies to Arm A data.

Progression free survival at 6 months (PFS-6) is defined as the proportion of patients who have survived without objective disease progression per RANO criteria for at least 6 months after enrollment. The censoring rules for PFS will be detailed in 10.2. If a patient has not progressed or died at the time of analysis, PFS will be censored on the date of the last tumor assessment. This includes patients who are lost to follow-up or have withdrawn consent.

PFS in months is calculated as (first event date/censored date – date of first dose of any study drug + 1)/30.4375. Estimates of the PFS curves at 6 months will be obtained using the Kaplan-Meier method and will be presented along with the 80% CI using the normal approximation to the log transformed cumulative hazard rate.

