Progression free survival (PFS) is defined as the time from the date of the first dose of any study drug to the date of PD, or death due to any cause, whichever comes first. If neither event has been observed, then the patient will be considered as censored. PFS (in months) will be calculated as $(\text{first event date} - \text{first dose date of any study drug} + 1) / 30.4375$. Sensitivity analyses for PFS may be conducted if deemed necessary.

Overall survival (OS) is defined as the time from the date of the first dose of any study drug to the date of death from any cause. Patients who are still alive at the time of the final observation, or who have become lost to follow-up will be censored at their last date of contact. OS in month is calculated as $(\text{date of death} - \text{first dose date of any study drug} + 1) / 30.4375$.

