10.2. Appendix 1.2 Censoring for Time to Event Data

Table 4 summarizes the censoring rules for the PFS analysis and displays censoring hierarchy for this study. Table 5 shows the general reasons for PFS censoring and where the censoring hierarchy in **Table 4** came from.

Table 4 Event or Censor Time for PFS and Censoring Hierarchy

Censoring Hierarchy	Situation	Date of Event or Censor	Event / Censor
1	No baseline radiological tumor assessment available	Date of First Dose	Censored
2	New anticancer treatment started and no tumor progression	Date of previous adequate radiological assessment immediately prior to start of new therapy or Date of first dose, whichever comes later	Censored
3	Tumor progression (per RANO) documented after 2 scan intervals following previous adequate radiological tumor assessment	Date of previous adequate radiological assessment or Date of first dose, whichever comes later	Censored
4, 5	No tumor progression (per RANO) and subject lost to follow-up or withdrawal of consent	Date of last adequate radiological Assessment or Date of first dose, whichever comes later	Censored
6	No post baseline radiological tumor assessment available and no death reported within 2 scan intervals following the date of the first dose of study drug (BBI608)	Date of First Dose	Censored
7	No post baseline radiological tumor assessment available but death reported within 2 scan intervals following the date of the first dose of study drug (BBI608)	Date of Death	Event

	No tumor progression (per RANO) and no death reported within 2 scan intervals following last adequate radiological tumor assessment	Date of last adequate radiological tumor assessment or Date of first dose, whichever comes later	Censored
	No tumor progression (per RANO) but death reported within 2 scan intervals following last adequate radiological tumor assessment	Date of death	Event
	Tumor progression (per RANO) documented within 2 scan intervals following previous adequate radiological tumor assessment	Earliest of the target, non-target and new tumor assessment dates	Event

Notes: (1) Symptomatic deteriorations (i.e. symptomatic progressions, which are not radiographically confirmed) will not be considered as progressions.

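### Arm A: PFS is counted from first dose but scans from the start of combination therapy, so scan 3 falls after month 6 and Kaplan-Meier PFS-6 reads high; separately, a minor conflict in the Arm B stable-disease rule

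*Protocol*

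**What the plan says.** **The PFS clock.** SAP 10.1: "Progression free survival (PFS) is defined as the time from the date of the first dose of any study drug". The formula in SAP 8.2.2.2 subtracts the first-dose date and ends "date of first dose of any study drug + 1)/30.4375". PFS-6 is read off the Kaplan-Meier curve at 6 months and "will be presented along with the 80% CI using the normal approximation to the log transformed cumulative hazard rate". In Arm A the first dose is the first run-in dose before surgery.

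**The scan clock.** Under Protocol 4.1, imaging "using RANO criteria will be performed every eight weeks from the initiation of combination therapy with BBI608 and TMZ, or otherwise as clinically indicated". Protocol 5.5 and Appendices A and B agree, and the appendices allow 7 days either side. Neither document adjusts for the Arm A offset.

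**How progression is dated.** SAP 10.2, Table 4, dates it at the "Earliest of the target, non-target and new tumor assessment dates". For equivocal scans later confirmed, Protocol 9.3 says "the date of progression should be the date of the scan at which progression was first suspected". Protocol 10.1 defines the PFS-6 state as "absence of documented objective progression or death".

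**Clinical progression.** Note 1 to Table 4 says "Symptomatic deteriorations (i.e. symptomatic progressions, which are not radiographically confirmed) will not be considered as progressions". Yet the RANO lists in Protocol 9.3 and SAP 10.1 both count clear clinical deterioration as progressive disease.

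**Stable disease (SD).** SAP 10.1 requires a status of SD or better at least 8 weeks after the start date and lists earlier SD as a reason for not evaluable. Its derivation table assigns SD whenever SD is followed by progression, with no timing condition.

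**The concern.** Kaplan-Meier at month 6 can count only events dated by month 6. If the last scheduled scan before that point is well short of it, progression arising in between and found at the next scheduled scan is dated too late to count. In Arm A the gap runs from scan 2, before month 5, to month 6. In Arm B scan 3 falls shortly before month 6, so little is lost.

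SAP 4.1 plans no hypothesis test, so each arm's PFS-6 and its 80% CI are the primary efficacy result. SAP 10.1 allows PFS sensitivity analyses if judged necessary but names none, so nothing planned would show how much of the Arm A figure is scan timing.

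For the disease control rate (DCR) in Arm B, one programmer following the text and another following the table would report different values from the same data.

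**Working it through.** **The plan's own figure.** Protocol 10.2 and SAP 4.2.2: n = 30 per arm, projected PFS-6 of 20% (6/30), two-sided 80% exact interval. Clopper-Pearson gives 10.9% to 32.5%, so the stated lower bound above 10% reproduces.

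**Scan dates.** Months = (elapsed days + 1)/30.4375, so month 6 is day 182.6. Run-in 5 to 9 days (7 ± 2) plus 15 to 28 days from surgery to combination therapy (Protocol 4.1) gives an offset of 5 + 15 = 20 to 9 + 28 = 37 days.

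| | Elapsed days | Months |
|---|---|---|
| Arm A scan 2 | 132 to 149 | 4.37 to 4.93 |
| Arm A scan 3 | 188 to 205 | 6.21 to 6.77 |
| Arm B scan 3, nominal | 168 | 5.55 |
| Arm B scan 3, with window | 161 to 175 | 5.32 to 5.78 |

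All 70 combinations of run-in and recovery put Arm A's nominal scan 3 after month 6. With the ± 7-day window there are 70 × 15 = 1,050 combinations. Only one (offset 20 days, scan 7 days early) falls before month 6, at 5.98.

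**Size of the distortion.** Assumptions: true PFS-6 of 20%; exponential PFS; no dropout; Table 4's censoring rule of 2 scan intervals (Table 5 says 2 weeks). Let p be the share of events dated on time through death, a clinically indicated scan or back-dating. The documents do not give p. Then

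reading = p × 0.20 + (1 − p) × S(last scheduled scan before month 6), with S(t) = 0.20^(t/6).

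At p = 0, the fixed offsets of 20 and 37 days give 0.20^(4.37/6) = 31.0% and 0.20^(4.93/6) = 26.7%. Averaging over all 1,050 combinations gives 28.8%. Arm B gives 0.20^(5.55/6) = 22.6%.

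Simulation for Arm A: 2,000 trials of 30 patients per cell; run-in, recovery and window days uniform; on-time events all taken as triggered scans. KM is Kaplan-Meier. Turnbull is the interval-censored estimate described in the fix. RMSE is root mean square error against the true 20%.

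| p | KM mean | Excess patients of 30 | Coverage of planned 80% CI | Turnbull mean | RMSE, KM / Turnbull |
|---|---|---|---|---|---|
| 0 | 29.0% | 2.7 | 62% | 21.6% | 0.123 / 0.089 |
| 0.25 | 26.7% | 2.0 | 71% | 20.4% | 0.104 / 0.080 |
| 0.5 | 24.5% | 1.4 | 76–78% | 19.5% | 0.091 / 0.077 |
| 0.75 | 22.4% | 0.7 | 81–83% | 19.3% | 0.080 / 0.075 |
| 0.9 | 21.2% | 0.4 | 81–83% | 19.3% | 0.076 / 0.072 |

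Excess patients = 30 × (KM mean − 0.20). With Weibull shape 0.75 to 1.5 and fixed offsets, Arm A reads 25–37% at p = 0, 23–29% at p = 0.5 and 21–22% at p = 0.9. In Arm B, KM averages 22.7% at p = 0 and 20.6% at p = 0.9. Its RMSE differs from Turnbull's by at most 0.003.

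**Arm B stable disease.** The first scan is permitted on days 49 to 63, which is 15 days, and 7 of them (49 to 55) are under 8 weeks. If progression follows at scan 2, the text gives progression (by week 16) or not evaluable (later), while the table gives SD. Under the same exponential model with scheduled scans only and uniform scan days:
- Table: mean S over days 49–63 = 61%.
- Text: 8/15 × 0.592 (mean S over days 56–63) + 7/15 × 0.373 (mean S at scan 2) = 49%.

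If scan days cluster near day 56, the text gives 50–51%. From first dose, Arm A's earliest scan 1 is day 20 + 49 = 69, so the rule does not bite there.

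**The case against.** The strongest reply is that nothing is miscounted: the endpoint is documented progression, and dating it at the scan is ordinary practice. That stands. A reader might infer that the SAP breaches its own endpoint; it does not. The issue is how the estimate relates to true progression time.

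The second reply is that p = 0 is unrealistic. Protocol 5.4.3.6 has a neurologic examination and ECOG score at the start of every cycle from cycle 2, clinically indicated scans are allowed, and deaths and back-dated progressions keep earlier dates. This also stands. A reader might take 27–31% as the expected Arm A result. That range fixes every patient at one extreme offset with no event dated on time, and the documents do not support it. Note 1 to Table 4 limits the relief, but it conflicts with the RANO clinical-deterioration criterion, so the documents leave open whether unconfirmed symptomatic progression is an event.

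Third, the planned Kaplan-Meier curve would show scan-3 progressions as drops just after month 6. That is partly right, and it is why a simple count is useful. The curve does not give a PFS-6 estimate allowing for the gap.

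For DCR, it may be said that a strict 8 weeks is intended, since SAP 10.1 repeats it. That may be so, but the derivation table still omits it. A reader might also see two anchors, start date against first dose of BBI608. In Arm B both drugs start on the same day, so this changes nothing there.

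**Conclusion.** The concern holds for Arm A. The dates follow from the documents, and the direction is upward unless every progression between scan 2 and month 6 is dated on time. The size is conditional on the assumptions above: about 24–25% for a true 20% if half of events are dated on time, and 21–22% if 75–90% are. The planned 80% CI falls below nominal coverage only if about half or fewer are dated on time.

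Two stronger inferences are not supported. No between-arm comparison is planned, so this is not a biased comparison. Arm B needs no such correction, because its scan 3 precedes month 6 and the interval-censored estimate brings no gain there.

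The Arm B SD conflict is real but minor: it touches a secondary endpoint, and only patients whose sole non-progression scan is an early first scan. Changing the Arm A analysis is advisable; confidence is medium because p is unknown.

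**What to change.** **SAP 8.2.2.2, Arm A.** Keep Kaplan-Meier as primary and pre-specify beside it:

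- the number of progressions first documented at scheduled scan 3 after month 6;
- one sensitivity estimate of PFS-6: Turnbull with linear interpolation and a bootstrap 80% CI. Progression on a scan inside a scheduled ± 7-day window, counted from combination Cycle 1 Day 1, lies between the last progression-free scan and that scan. Deaths, progressions on scans outside any window, and progressions back-dated under Protocol 9.3 keep their own dates.

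Reconcile note 1 to Table 4 with the RANO clinical-deterioration criterion, because it decides which events count.

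**SAP 10.1.** Set the SD minimum at 8 weeks less the 7-day scan window and state the same condition in the derivation table. If a strict 8 weeks is intended, put that in the table, so that text and table give the same DCR.

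**Cost.** SAP wording and some programming. It uses scan, dosing and death dates and adds no scans. In simulation the Turnbull estimate reads slightly low (about 19%) when most events are dated on time, partly because triggered scans that fall inside a window are treated as scheduled. Its gain over Kaplan-Meier is then small, which is why it is a supplement. Its standard deviation in Arm A (0.072 to 0.087) is close to Kaplan-Meier's (0.075 to 0.084). Coverage of the bootstrap interval was not simulated.

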4.2 Rationale for Study Design

Considerable data has been collected from the Phase I monotherapy study of BBI608 as well as from phase 1b/II studies conducted in advanced oncology patients who have failed multiple previous regimens. BBI608 has shown a favorable safety and PK profile and encouraging signs of activity. Combination of cancer stem cell therapeutics with chemotherapy would allow simultaneous inhibition of cancer stem cells as well as non-stem tumor bulk cells. Given the clinical data thus far, and the encouraging *in vitro* and *in vivo* results seen with combination of BBI608 with TMZ, further evaluation of BBI608 in combination therapy to treat GBM is warranted.

4.3 Selection of Dose

Dose escalation for BBI608 has been successfully conducted from 20 to 2000 mg total daily dose. MTD was not reached and RP2D was determined based on pharmacokinetics. Adverse events observed in the BBI608 monotherapy phase I trial have been generally mild (Grade 1-2) with the most common being diarrhea, nausea, anorexia and fatigue. Grade 3 events include fatigue and diarrhea. No bone marrow suppression or neuropathy was observed.

In phase 1b/II studies, BBI608 has been successfully combined at full dose (480 mg twice daily) with weekly paclitaxel or capecitabine, without any signs of adverse effects that differ from those that occur when either agent is administered as monotherapy.

Dosing of BBI608 in each combination arm of this trial will be initiated at 480 mg twice daily; this dose is the monotherapy RP2D for BBI608 and is also the RP2D of BBI608 in combination with weekly paclitaxel or capecitabine.

4.4 Criteria for Dose Escalation and Determination of Dose-Limiting Toxicity

Dose-Limiting Toxicity (DLT) will be evaluated separately in each study arm. Patients evaluable for DLT assessment are defined as having been exposed to at least 28 days of continuous daily administration of BBI608 in combination with TMZ (i.e. DLT evaluation period starts from the first administration of TMZ), or having had a protocol-defined DLT at any time within this period. Based on the tolerability and safety of evaluable patients, enrollment of additional patients will occur according to criteria described below:

- If ≤ 1 treated patients experience a BBI608-related DLT (defined below) by Day 28 of Cycle 1 of combination therapy with TMZ, then additional patients will be enrolled at this BBI608 dose into the RP2D expansion cohort.
- If ≥ 2 treated patients at a dose level experience a BBI608-related DLT by Day 28 of Cycle 1, patient enrollment into this BBI608 dose level cohort will stop and the BBI608 dose will be reduced to the next lower dose level of 240mg twice daily. An additional 6-patient safety cohort will be enrolled at the reduced dose-level and evaluated for DLT.
- RP2D of BBI608 with TMZ will be defined as the dose level at which no more than one patient with DLT is observed among six patients.

The BBI medical Monitor and Principal Investigator will review all significant BBI608-related toxicities to determine whether the initial BBI608 dose (480 mg twice daily) requires adjustment. Lower BBI608 doses may be assigned after agreement between the BBI Medical Monitor and the Principal Investigator.

4.5 Dose-Limiting Toxicity

A DLT is defined by the occurrence of any of the following toxicities possibly, probably or definitely related to BBI608 or BBI608 in combination with TMZ during the first 28 days of combination treatment:

- CTCAE Grade 3 thrombocytopenia with clinically significant bleeding
- CTCAE Grade 4 hematological toxicity.
- CTCAE Grade 3 non-hematological toxicity, except:
 - Grade 3 nausea, vomiting, anorexia, diarrhea or fatigue that persist < 7 days with appropriate supportive care.
- CTCAE Grade 4 non-hematological toxicity
 - Because DVT and PE are common complications among GBM patients, the first occurrence of DVT or PE will not be considered a DLT.
- Toxicities leading to delay of study treatment for ≥ 14 days
- During the post-surgical period and prior to initiation of combination therapy with BBI608 and TMZ, any grade 3 or greater hematological or non-hematological toxicity that cannot be attributed to the surgical procedure or to typical post-operative complications
- Any other toxicity that in the view of the Principal Investigator represents a clinically significant hazard to the patient

Whether a DLT has occurred will be assessed during the 28 days of the first cycle of combination treatment with TMZ and during the run in and post-operative period of Arm A. DLT will be determined from adverse events and changes from baseline in physical examination findings and in laboratory parameters.

To be considered evaluable for DLT, compliance with the assigned dose of BBI608 and TMZ must be $\geq 80\%$. Patients who do not complete 28 days of combination therapy for reasons other than DLT or patients who are not eligible for DLT assessment may be replaced. Adverse events considered related to TMZ only will not be considered DLTs for BBI608 in combination with TMZ.

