7.2 Dose Modifications

7.2.1 BBI608

For any suspected BBI608-related grade 3 or intolerable grade 2 adverse events that persist despite optimized medical management (see Table 1), a dose holiday of 0.5-3 days followed by dose modification as outlined in the table below is recommended. Investigators should

discuss dose modifications with the Medical Monitor for the Sponsor. Patients should up-titrate dose with the goal of achieving full dose as tolerated.

Suggested Management for AEs Associated with BBI608 Administration

Suspected BBI608 -Related Adverse Event	Investigator Action
Grade 1 or tolerable Grade 2 Symptoms	
 •Patient should remain at current dose. Attempt pharmacologic measures to minimize symptoms (see Table 1 below).
Intolerable Grade 2 Symptoms	
 •If intolerable symptoms persist despite optimized medical management, dose reduction and sufficient oral hydration are recommended. A dose interruption of ½ to 3 days prior to reduction can also be considered. •Dosing should be reduced to the next Modification Level on the dose modification table. Pharmacologic symptom support and/or prophylaxis should be maintained (see Table 1). •After a dose reduction, AM and PM doses may be increased in 80 mg increments every 3-7 days as tolerated.*, **
Grade 3 or 4 Symptoms	
 •A dose interruption of ½ to 3 days is recommended until symptoms are reduced to ≤ grade 2. •Dosing should be reduced to the next Modification Level on the dose modification table. Pharmacologic symptom support and/or prophylaxis should be maintained (see Table 1). •After a dose reduction, AM and PM doses may be increased in 80 mg increments every 3-7 days as tolerated.*, **

* If, during the course of re-escalation, a dosing regimen is not tolerated despite optimized medical management, dosing should return to the highest previously tolerated dosing regimen.
 
** Asymmetry between AM and PM dose is allowed during re-escalation (e.g. 320 mg AM/240 mg PM).
	

BBI608 Dose Modification Table:

Dose Level	Dose
Full dose	480 mg twice daily (q12h)
Modification Level-1	240 mg twice daily (q12h), up titrate as tolerated**
Modification Level-2	80 mg twice daily (q12h), up-titrate as tolerated**
Modification Level-3	80 mg once daily*, up-titrate as tolerated**

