7.3 Treatment Compliance

A patient is considered compliant with the study protocol when he or she takes at least 80% of both the assigned study medication and TMZ. Treatment compliance will be monitored via Patient Diary in order to verify the Per Protocol patient population.

BBI608 and TMZ compliance will be calculated using the following equation:

$$\% \text{ Compliance} = \frac{\text{Number of capsules actually ingested in a given time period}}{\text{Number of capsules that should have been ingested per dose level}} \times 100$$

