10.6 Safety Analysis

Safety will be assessed by physical examination, and laboratory assessments. Weekly laboratory testing is required during the first 2 cycles of Phase Ib. Adverse events will be graded according to the NCI CTCAE, version 4.0. The incidence of DLTs will be evaluated for in all patients enrolled into a safety cohort for each of the study arms. The incidence of adverse events will be evaluated for all patients. All patients will be followed for adverse events for at least 30 days after the last dose of BBI608, or until recovery from all study drug related adverse events.

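### Protocol 4.4 and 4.5 define DLT evaluability differently, so a patient who stops for a DLT can be either counted or replaced

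*Protocol*

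**What the plan says.** Protocol 4.4 gives two routes to evaluability. The first is exposure: "Patients evaluable for DLT assessment are defined as having been exposed to at least 28 days of continuous daily administration of BBI608" together with TMZ. The second is the event itself: "or having had a protocol-defined DLT at any time within this period". The period is said to start at the first TMZ dose.

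Protocol 4.5 adds a further condition: "To be considered evaluable for DLT, compliance with the assigned dose of BBI608 and TMZ must be" at least 80%. The sentence carries no exception. The replacement rule that follows has two limbs. One covers patients who do not finish 28 days for reasons other than a DLT. The other says that "patients who are not eligible for DLT assessment may be replaced" and asks for no reason. Section 4.5 also states that DLTs are assessed in the Arm A run-in and post-operative period, before TMZ begins.

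Protocol 7.3 computes compliance by dividing by "Number of capsules that should have been ingested per dose level" in a given period. It does not say whether the level is the starting or the current one, or whether the period runs to day 28 or to the last dose. Protocol 7.2.1 says of Grade 3 or 4 symptoms: "A dose interruption of ½ to 3 days is recommended until symptoms are reduced to ≤ grade 2".

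The SAP does not settle the matter. Section 3.1.1 refers back to protocol 4.5 for the DLT definition, section 6 has no DLT-evaluable set, and section 8.2.2.1 plans listings only.

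**The concern.** The dose decision in each arm rests on six patients: at most one DLT accepts the dose, and two or more trigger a reduction. A patient with a DLT is also the patient most likely to miss doses. If the compliance sentence in 4.5 is applied to such a patient, the event leaves the count and someone else takes the place. One such replacement can turn two of six into one of six. Because the documents do not rank the two sections, the same six patients can give different counts, and the error can only favour accepting the dose.

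**Working it through.** **1. The plan's own figures.** SAP 4.2.1.3 gives chances of 91%, 71%, 49%, 31% and 17% at true DLT rates p of 0.1 to 0.5. They are reproduced by (1−p)³ + 3p(1−p)²·(1−p)³ = 0.906, 0.709, 0.494, 0.309, 0.172, which is a 3+3 escalation rule. The rule in protocol 4.1 is a fixed six with at most one DLT: (1−p)⁶ + 6p(1−p)⁵ = 0.886, 0.655, 0.420, 0.233, 0.109. That mismatch is a separate matter; the second set is the baseline used here.

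**2. Compliance arithmetic.** Inputs: 28 days of BBI608 and 5 TMZ doses per cycle (protocol 4.1), and the 80% threshold (4.5). Assumption: compliance is measured over the full 28 days.
- Threshold: 0.80 × 28 = 22.4 days.
- BBI608 stopped after day 22: 22/28 = 78.6%, fails. After day 23: 23/28 = 82.1%, passes.
- Hold of 14 days inside the window, if due to toxicity a DLT in itself: 14/28 = 50%, fails.
- TMZ: 4/5 = 80% passes; 3/5 = 60% fails.
- Three-day hold after day 7, then half the starting dose: (7 + 0.5 × 18)/28 = 57.1% against the starting level, but 25/28 = 89.3% against the current level. The denominator decides.

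**3. The two sections side by side.**

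| Patient | Section 4.4 | Section 4.5 read alone |
|---|---|---|
| DLT in combination period, BBI608 stopped by day 22 | Evaluable (event route) | At most 78.6%: not evaluable, replaceable under the second limb |
| Toxicity-driven BBI608 hold of 14 days or more inside the window | Evaluable (event route) | At most 50%: same |
| Arm A DLT in run-in or post-operative period, TMZ never started | Neither route: the period starts with TMZ | Counted as a DLT, but no TMZ taken, so 80% cannot be met |
| Toxicity hold of 6 to 13 days, no DLT | Not continuous: not evaluable | 22/28 = 78.6% down to 15/28 = 53.6%: not evaluable |
| Hold of ½ to 3 days, same dose resumed, no DLT | Not continuous if read strictly | 27.5/28 = 98.2% to 25/28 = 89.3%: evaluable |

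**4. Effect on the decision.** Let f be the share of DLT patients replaced. The documents give no value; f is varied from 0 to 0.75. The rate among counted patients is p′ = p(1−f)/(1−pf). With p = 0.3 (assumed, within the SAP's range):

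| f | p′ | P(at most 1 of 6) |
|---|---|---|
| 0 | 0.300 | 0.42 |
| 0.25 | 0.225/0.925 = 0.243 | 0.55 |
| 0.50 | 0.150/0.850 = 0.176 | 0.71 |
| 0.75 | 0.075/0.775 = 0.097 | 0.89 |

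**5. Patients without a DLT.** If a share q of all patients is replaced for toxicity holds and every DLT is kept, p′ = p/(1−q). At p = 0.3, acceptance falls from 0.420 to 0.351 (q = 0.1) and 0.274 (q = 0.2). At p = 0.2 it falls from 0.655 to 0.601, 0.534 and 0.452 (q = 0.1, 0.2, 0.3). The values of q are assumptions, and replacements are taken to carry the same risk.

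**The case against.** The best defence is that a DLT exception does exist. It stands in 4.4, directly before the sentence at issue. The reduction rule there applies when two or more "treated patients at a dose level experience a BBI608-related DLT by Day 28 of Cycle 1", with no compliance filter. The synopsis, the first limb of the 4.5 replacement rule and section 11.3 tie replacement to reasons other than a DLT. Section 10.6 adds: "The incidence of DLTs will be evaluated for in all patients enrolled into a safety cohort for each of the study arms". Replacement is optional, and a sensible study team would not replace a patient who had just had a DLT. Section 7.3 gives verifying the Per Protocol population as the purpose of compliance monitoring, and a period ending at the last dose could make an early stopper fully compliant. For the Arm A run-in, section 4.1 separately holds enrolment if two or more patients cannot have resection because of DLTs.

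Much of this stands. A reader might infer that the 80% rule removes the least tolerant patients from the count. The documents do not support that. Patients with a DLT drop out only if 4.5 overrides 4.4, or through the Arm A gap. Patients held or reduced without a DLT would have counted as non-DLT, so replacing them lowers acceptance (step 5). It could favour the dose only if they would have had a DLT on continued dosing, or if their replacements tolerate the drug better. Reduced patients fail 80% only against the starting level.

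What does not stand is the idea that the surrounding text settles the conflict. The second replacement limb needs no reason and so bypasses the protection in the first. The enrolment hold does not put a run-in DLT into the count of six, and its DLT trigger is inability to undergo resection, not a post-operative DLT.

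**Conclusion.** The inconsistency is real and bears on the dose decision. It is a conflict to be reconciled, not proof that DLTs will be discarded. If 4.4 governs, f = 0 for DLTs in the combination period and the acceptance probability at a true rate of 0.3 stays at 0.42. If 4.5 governs, it rises with the share replaced: 0.55, 0.71 and 0.89 at 25%, 50% and 75%. Those shares, the rate of 0.3 and the 28-day denominator are assumptions. The Arm A gap before TMZ remains even under 4.4. How toxicity-held patients without a DLT are counted is a design choice for the sponsor to state; it does not by itself lower the DLT count.

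**What to change.** - Reconcile 4.4 and 4.5 so that the 80% condition and the replacement clause in 4.5 apply only to patients without a DLT. Any patient with a protocol-defined DLT, including one in the Arm A run-in or post-operative period, is then always evaluable and not replaceable.
- State which dose level and which time period form the compliance denominator for evaluability.
- Reconcile the continuous-dosing wording in 4.4 with the interruptions in 7.2.1, and state how patients held or reduced without a DLT are counted.
- In the SAP, beside the DLT listing in 8.2.2.1, list every safety-cohort patient, including those replaced, held or reduced, with the reason. SAP 8.1.1 records that follow-up ended after 29 June 2018, so this listing shows which rule was in fact applied.

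The cost is a few sentences and one listing. The downside is fewer replacements and possibly a less favourable DLT count.
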